## 1.0 Objectives

#### 1.1 Study Objectives

Describe the purpose, specific aims or objectives. State the hypotheses to be tested. Describe the treatment that is considered standard of care (i.e., indicate how patients would be treated in a non-investigational setting). Indicate if the study test article(s) is available to patients without taking part in the study.

The overall aim of this study is to conduct a formal, real world test of the efficacy of Family-centered function-focused care (Fam-FFC) on patient and caregiver-centered outcomes in community-dwelling, hospitalized older adults with very mild to moderate dementia.

Aim 1: Validate the efficacy of Fam-FFC on physical function (ADLs/ performance and physical activity), delirium occurrence and severity, behavior, and mood.

**H1**: Patients exposed to Fam-FFC will demonstrate more return to baseline ADL function as compared to those in the control condition.

**H2:** Patients exposed to Fam-FFC will demonstrate increased physical activity, improved chair rise and less delirium occurrence and severity, less NPS, and less depression, as compared to those in the control condition.

Aim 2: Evaluate the impact of Fam-FFC on CG –centered outcomes.

**H3:** CGs exposed to Fam-FFC will demonstrate improved preparedness for caregiving, and less strain, burden, and desire to institutionalize as compared to those in the control condition.

Aim 3: Evaluate the relative costs for Fam-FFC v. control condition, and calculate health care (post-acute health care utilization) costs and total cost savings for Fam-FFC.

 $H_4$ : Patients exposed to Fam-FFC will demonstrate higher intervention costs but lower post-discharge cost for health care services (emergency room admissions, hospital admissions, and long-term nursing home admissions) as compared to those in the control condition.

**H**5: Patients exposed to Fam-FFC will demonstrate total cost savings overtime as compared to those in the control condition.

Exploratory Aim: Assess the cultural appropriateness of Fam-FCC for diverse families.

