## 2.0 Background

#### 2.1 Scientific Background and Gaps

Describe the scientific background and gaps in current knowledge.

Persons with Alzheimer's disease and related dementias (ADRD) account for 3.2 million hospital admissions per year and are about two times more likely to be hospitalized than their peers who are cognitively healthy. Once hospitalized, individuals with ADRD are more likely to experience potentially preventable complications such as delirium, neuropsychiatric symptoms (NPS), pressure ulcers, falls, and nutritional deficiencies. The unfortunate consequences of this combination of factors is that persons with ADRD often have clinically significant functional decline resulting in increased risk for hospital readmission, emergency department use, morbidity, earlier mortality, and long-term care placement. 

Prior to hospitalization, approximately 75% of hospitalized patients with ADRD are living at home and receiving care from family members or friends,  Upon hospitalization, the goal of most families is to have their relative return home.  However, family caregivers (CGs) are limited in the amount of physical care they can provide in terms of lifting, moving and providing incontinence care.  The additive stress of the hospitalization, and the patient's increased functional dependency, often co-existing with persistent delirium, compounds the strain of the family CG,  prompting the decision to seek long-term nursing home care.  It is particularly important, therefore, that patients with ADRD receive the type of care, beginning at admission and continuing through the post-acute transitional period, that optimizes function and physical activity and helps prevent or decrease functional decline.

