Depression	Cornell Scale for Depression in Dementia (CSDD) 	A 19-item survey designed to assess depressive symptoms in individuals with dementia. 154, 155 There is sufficient evidence of reliability and validity. 155	
NPS	Brief Neuropsychiatric Inventory (NPI-Q) 	A 12-item, reliable, validated informant-based assessment of neuropsychiatric symptoms and associated caregiver distress. 156	

Adverse Events	Report of falls, hospitalizations,	A monthly check of the patient hospital record to evaluate for
	transfers to the emergency	hospitalizations/ED visits (in addition to the family caregiver
	department	report at month 2 and month 6).

The following outcome measure data collection will be initiated within 72 hours of discharge (T1), and 2 month (T2) and 6 month post-discharge (T3), by research evaluators via interview of the patient/family CG

Family Caregiver Outcome Measures- collected for both control and intervention group.			
Aim 2: Evaluate the imp	Aim 2: Evaluate the impact of Fam-FFC on Family CG-centered outcomes.		
	All measures are self-rated and will be initiated within: 72 hours of discharge (T1), 2 (T2) and 6 months post-discharge (T3). This data is collected via pen/paper tools completed by family CG.		
Measure	Measure Tool Description		
Preparedness for caregiving	Preparedness for Caregiving Scale 	An 8-item instrument that asks caregivers how well prepared they believe they are for multiple domains of caregiving: physical care and emotional support, setting up support services, dealing with the stress of caregiving. Items are rated 0 (not at all prepared) to 4 (very well prepared); shows very good reliability and internal consistency, 157 including in family CGs of hospitalized persons with dementia. 59	
Caregiver Strain	Modified Caregiver Strain Index (CSI) 	A 13-question tool that measures strain (financial, physical, social, psychological, and personal) related to care provision, with excellent internal consistency and reliability. 158,159	
Caregiver Burden	Zarit Burden Interview (ZBI-12)  short version	12-item tool that measures caregiver perception of burden has shown high internal consistency and discriminative ability in caregivers of persons with dementia. 160,161	
Desire to Institutionalize	Desire to Institutionalize Scale 	6-item scale with moderate reliability; Cronbach alpha = 0.694.162	

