Cost Outcomes Aim3: Evaluate the relative costs for Fam-FFC v. control condition; calculate health care cost (post-acute health care utilization) and total cost savings for Fam-FFC. We have developed cost-related data collection forms, specifically Activity Diaries, to help facilitate data collection for the champions, research nurse facilitators, and staff. These include staff and research nurse time and hours worked, training time (including replacement), supplies, and incentives. Post—acute utilization will be evaluated with a cumulative count of emergency room visits, number/days of hospitalizations, and long-term nursing home admissions six months after discharge, obtained from questioning of the family at each point of data collection. Health care unit charges and reimbursement rates will be obtained from yearly publications from the American Hospital Associations and other health data organizations.

Treatment Fidelity. Treatment fidelity will be evaluated with regard to delivery of the intervention, receipt, and

enactment as shown in Table 5. Assessment of Environment and Policy will be conducted by the Fam-FFC Research Nurse with champions as part of the intervention (See Component 1). Knowledge of Fam-FFC is a valid and reliable 15-item paper and pencil multiple choice exam that tests staff knowledge about Fam-FFC. The Goal Attainment Scale  evaluates attainment of up to four patient goals and will be completed by the Fam-FFC Research Nurse with input from CGs, champions, nursing staff, and other health care professionals who work with the patient. This will be reviewed at discharge and post-discharge data collection points. The FamPath Audit tracks delivery of FamPath and Family CG Activity Logs monitor CG involvement and agreement with the care plan. The Function Focused Care Behavior Checklist (FFC-BC) is a valid and reliable objective measure including a 19-item checklist reflecting nursing staff performance of Fam- FFC. Oversight of treatment fidelity will be provided by the co-investigator (BR) who will collaborate with the research team to ensure adherence to the study manual of operations and standardization across sites. See below for a comparison of treatment fidelity for treatment and control sites.

Treatment Fidelity (Bolded items: both treatment and control sites; items not bolded: treatment site only)		
Focus	Data (Appendix B)	Evidence of Treatment Fidelity

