Aim 3: Evaluate the relative costs for Fam-FFC v. control condition, and calculate health care and total cost savings for Fam-FFC. Standard micro-costing methods will be used to estimate costs. Using the guidelines offered by Chatterji and colleagues, 191 total intervention costs will be based on expenditures/outlays for each of the following: (1) intervention; (2) consultant fees; (3) personnel costs, (4) incentives, meals, travel for study participants; (5) utilities, maintenance, security and other operating costs; and (6) administrative costs. We will identify all of the "inputs" that go into the implementation and then assign unit costs to these inputs (wages/salaries acquired from the unit managers, cost of materials, etc.). Then, we will multiply the units of inputs by their unit costs and sum this across all of inputs to determine the total cost of implementation per setting. An average across all settings will then be calculated. To estimate the cost of healthcare for each group, we will collect unit costs from existing literature including data published yearly by the American Medical Association, the American Hospital Association, the National Hospital Discharge Survey, and the American Managed Behavioral Healthcare Association. Similarly, these unit cost estimates for each type of health care utilization (emergency room, hospital and long-term nursing home admissions) will then be multiplied by the number of units used by each individual in the sample. A variable will be created for total health care cost by summing across conditions while exercising care to avoid any double counting of services. Health care and total cost savings will be calculated for each treatment condition. Mean costs and savings will be computed and subsequently tested for statistical significances across conditions using a t-test. In calculating cost we will also take into account fixed versus variable costs adjusting for variation over time in wages, benefits, and supplies using a standard micro-costing approach. We will then use multivariable regressions to determine whether Fam-FCC is significantly related to lower costs of healthcare and total cost savings controlling for covariates. Moreover, we will compare health care costs in terms of changes over time with paired t-test (within group differences) and with parametric Analysis of Variance (between group differences).

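### Aim 3 costs long-term nursing home use by admissions, not days, so delay of placement within six months is not seen and delay past month 6 always counts as one full unit

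*Combined protocol and SAP*

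**What the plan says.** Section 7.2, Data Collection (Cost Outcomes, Aim 3), defines post-acute utilization as a running count of visits to the emergency room, "number/days of hospitalizations, and long-term nursing home admissions six months after discharge". The source is family report, "obtained from questioning of the family at each point of data collection".

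Section 8.3 (Aim 3) sets the costing rule. It takes "unit cost estimates for each type of health care utilization (emergency room, hospital and long-term nursing home admissions") and says that these "will then be multiplied by the number of units used by each individual in the sample". It does not define the nursing home unit further. Mean costs are then compared by t-test and by multivariable regression.

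H4 in section 1.1 uses the same measure: "lower post-discharge cost for health care services (emergency room admissions, hospital admissions, and long-term nursing home admissions"). H5 then tests total cost savings. Section 1.2 lists health care cost and total cost savings among the primary endpoints.

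The only planned record search is in the adverse event row of the section 7.2 outcome table: "A monthly check of the patient hospital record to evaluate for" hospitalizations and emergency visits. It does not cover nursing home stays. Discharge disposition is abstracted at the end of the index stay, but neither section 7.2 nor section 8.3 links it to the cost count.

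**The concern.** A long-term placement is open-ended, so its cost inside a fixed follow-up is set mainly by how long the patient is there. The plan collects days for hospital stays but not for this service.

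Timing is also something the intervention could plausibly change. Section 2.1 describes functional dependency and caregiver strain as "prompting the decision to seek long-term nursing home care", and Fam-FFC is meant to act on both. If it postpones some placements, the postponed days are part of the saving that H4 and H5 are meant to detect. A count of admissions registers such a change only when it carries the placement across the six-month line.

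**Working it through.** The documents state no nursing home cost, placement rate or placement date, so there is no figure to reproduce. The check applies the section 8.3 rule to simple cases and compares it with a rule based on days.

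**Inputs**
- Units: admissions (sections 1.1, 7.2 and 8.3).
- Follow-up: six months (section 7.3). The length in days is not given; 180 to 183 is assumed.
- Each placed patient is assumed to stay in the home to the end of the window.
- Price per day: not in the documents; USD 100 to 400 is assumed, for illustration only.

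**Step 1: two placements inside the window**
- Count rule: day 10 = 1 unit, day 170 = 1 unit, difference 0.
- Days rule, 180-day window: 180 − 10 = 170 and 180 − 170 = 10. The ratio is 17.0 and the difference 160 days.
- Days rule, 183-day window: 173 and 13. The ratio is 13.3 and the difference is again 160 days.
- At the assumed prices, 160 days is worth 160 × 100 = USD 16,000 to 160 × 400 = USD 64,000. The count rule records 0.

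**Step 2: what the count credits when placement is delayed (180-day window)**

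| Placement moves | Units saved (count) | Days saved |
|---|---|---|
| day 10 to day 170 | 0 | 160 |
| day 10 to after month 6 | 1 | 170 |
| day 170 to after month 6 | 1 | 10 |

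The same credit of one unit covers 10 days and 170 days, while 160 days can earn none.

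**Step 3: when this distorts the comparison of arms**

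Let arm k have N_k placements per patient with mean in-window stay L_k. Let p be the price per day and c the unit cost per admission.
- Days rule: p(N_1·L_1 − N_0·L_0).
- Count rule: c(N_1 − N_0).
- Set c = p·L_0, so that the control arm is priced correctly. The days difference minus the count difference is then p·N_1·(L_1 − L_0).

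With that calibration the error vanishes if mean in-window stay is equal in the two arms, and not otherwise.

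**Step 4: an illustration**

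Assume control placements spread evenly over 183 days and a uniform 60-day delay under Fam-FFC.
- Placements pushed past the window: 60/183 = 33%. The count credits 0.33 unit per control placement.
- True in-window saving: the first 123 days of placements save 60 days each, and the last 60 save 30 on average. (123 × 60 + 60 × 30)/183 = 9,180/183 = 50 days.
- If one unit is priced at the control arm's mean in-window stay, 183/2 = 91.5 days, the credit is 91.5 × 60/183 = 30 days against a true 50.
- The two agree only if one unit is priced at 50.2 × 183/60 = 153 days. A dearer unit would overstate the saving.

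Even in this simple case, the direction of the error depends on a unit cost that the documents do not give.

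**The case against.** The best defence is that section 8.3 leaves the nursing home unit open, and that in section 7.2 the words about number and days could be stretched to govern nursing home admissions as well. Published prices might also be per day. The unit is indeed undefined. But the punctuation ties days to hospitalizations, three sections say admissions, and on the generous reading a per-day price would still have no dates or length of stay listed to work from.

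A second objection is that an average cost per admission may misprice individuals without biasing the comparison of arms. That stands: Step 3 shows that, with a well-calibrated unit cost, bias needs a difference between arms in in-window stay. Such a difference is plausible but not shown.

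The documents do not support four stronger inferences that a reader might draw:
- *Delayed placement saves nothing, or only complete avoidance is seen.* Delay past month 6 removes the admission from the count and saves a full unit.
- *The total cost result will be wrong by a known sum, or in sign.* Counts can be invented that reverse the sign, but no placement rate, date or price is given, so neither can be claimed.
- *Nursing home care is the largest cost item.* No section says so. The background text on placement concerns its causes, not its cost or timing.
- *Patients placed straight from the index stay are lost.* Discharge disposition is abstracted and families are questioned from T1, so these patients can be identified. What is missing is a sentence bringing them into the cost count.

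**Conclusion.** The point holds as a defect in how one cost component is measured. Followed as written, the plan gives equal cost to placements that differ about 13- to 17-fold in days (180- to 183-day window, patient staying to the end), and credits any delay past month 6 with one unit regardless of the days saved.

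If Fam-FFC alters the timing of placement, the H4 and H5 cost differences are misstated. Neither the size nor the direction can be computed from the documents, and the dollar figures and the 60-day example are illustrations on assumed inputs. The function, delirium, behavior, mood and caregiver hypotheses (H1 to H3) are untouched. This is a cheap improvement to Aim 3.

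**What to change.** 1. At T1, T2 and T3, add the start and end date of each long-term nursing home stay to the existing family questions.
2. Use the discharge-disposition abstraction already planned to count placements made directly from the index stay, with the discharge date as the start date.
3. In section 8.3, define the nursing home unit as days in long-term nursing home care from discharge to month 6, costed at a per-day rate from a named source. State the length of the window in days.
4. Report the number of admissions descriptively.
5. For patients already past follow-up, use the data collection interval in which the placement was reported as an approximate date, and say so in the report. The interval from T2 to T3 is four months, so a midpoint date can be out by up to two months, before allowing for the two-week visit windows.

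The cost is two added fields and a few sentences in section 8.3. The downsides are some family recall error in dates, and only approximate dates for the earlier sites. Section 8.2 already refers to the last site, so dates recorded prospectively can cover only the remaining patients.

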#### III. Data Collection

Patient data will be collected based on chart review, observations, actigraphy, and staff proxy informant interviews. Family CG data will be collected via electronic surveys on a tablet or by paper if a participant chooses. At all measurement time points, research evaluators will end data collection with the patient if he/she observes signs of dissent from the patient which includes: verbal refusal to answer a question, closing eyes and refusing to respond, asking the evaluator to leave, and moving away from the evaluator. The training of evaluators will include interrater reliability (minimum of 90%). Evaluators will not be informed of randomization results or provided with the details of the intervention. The research evaluators are fluent in Spanish and will use translated consents and study materials, in the event that Spanish is the primary language. The RedCap system will be used for screening of participants and data collection. The same data is collected on the intervention and control units. Descriptive (one-time) and outcome (multiple time-points) data are collected.

*Upon enrollment, within 48 hours of admission to the unit, patient and family CG descriptive measures* will be collected. Patient characteristics will include age, race/ethnicity, gender, marital status, education, medical diagnoses, medications, the use of sensory and mobility devices, and disease burden. Comorbid conditions will be classified with the *Charlson Comorbidity Index*.  Pre-admission function (ADL performance 2 weeks prior to admission) using the *Barthel Index*  (also an outcome measure) will be evaluated based on report from the family CG. Evaluation of hearing loss will be assessed using The Whisper Test. Pain will be measured using the Pain Assessment in Advanced Dementia and The Verbal Descriptor Scale. Upon discharge, length of stay, use of tethers (IV lines, pulse oximetry, urinary catheters, etc.), physical restraint use, and discharge disposition will be acquired. Cognitive *domains affected* by both dementia and delirium will be evaluated: executive function, orientation, memory, abstract thinking, and attention, evaluated by the subdomains of the *MoCA*.  The types of interventions provided on the FamPath assessment and care plan will be collected for descriptive purposes, extracted at the completion of the intervention.

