## 7.4 Test Article(s) (Study Drug(s) and/or Study Device(s))

#### 7.4.1 Description

Provide a brief description of all test articles (drugs (including any foods and dietary supplements), devices and/or biologics used in the research including the purpose of their use and their approval status with the Food and Drug Administration (FDA). Include information about the form of the drug product (e.g., tablets, capsules, liquid).

The **experimental condition**, Fam-FFC, will be coordinated and implemented by a Family-centered Function Focused Care Nurse (Fam-FFC Nurse), who will work in the treatment units 20 hours a week for 14 months to implement the four components of the intervention. In addition, the sites will identify two members of the nursing staff from each unit (one for day and one for evening shift) to be Family-centered Function Focused Function Focused Care Champions (Fam-FFC Champions). The four components of Fam-FFC include: **Component I-** Environmental and Policy Assessments; **Component II-** Education and Training of Nursing Staff; **Component III-** Ongoing Training and Motivation of Nursing Staff. The Fam-FFC Nurse will work with the champions to mentor and motivate nursing staff (RN, LPN, nursing assistants) to provide Fam-FFC by: (a) role modeling Fam-FFC, reinforcing performance of and benefits of Fam-FFC, and brainstorming about ways to overcome challenges; (b) highlighting staff role models and

positive opinion leaders; and (c) eliminating the influence of negative opinion leaders; **Component IV** Implementation of the FamPath Care Pathway which includes: (a) information on the admitting condition, diagnostics, and treatment, (b) family/patient education, (c) transitional hand-off to post-acute providers, and (d) post-acute follow-up to provide ongoing education and modification of the function-focused care plan.

The Attention Control condition (Fam- FFC Ed-only) consists of Component II, education of the nursing staff in participating hospital units (exactly as offered in treatment sites), and education of CGs about hospital orientation and reinforcement of discharge teaching (medications/treatments, medical follow-up). Research staff not familiar with Components I, III and IV will deliver the staff and CG education per manualized protocol.

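### H5 claims total cost savings without a formula, and the only utilization described for costing starts at discharge, so an index-stay difference would most naturally be left out

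*Combined protocol and SAP*

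**What the plan says.** Section 1.1 states H5 as a direction only: "Patients exposed to Fam-FFC will demonstrate total cost savings overtime as compared to those in the control condition". H4 is narrower. It expects higher intervention costs but "lower post-discharge cost for health care services (emergency room admissions, hospital admissions, and long-term nursing home admissions").

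Section 1.2 places costs among the primary endpoints and, like section 7.2, equates health care cost with post-acute use. The Aim 3 wording in 7.2 is to "calculate health care cost (post-acute health care utilization) and total cost savings for Fam-FFC", and the measure counts emergency visits, hospitalizations (number and days) and "long-term nursing home admissions six months after discharge, obtained from questioning of the family at each point of data collection".

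Section 8.3 (Aim 3) says that unit costs "for each type of health care utilization (emergency room, hospital and long-term nursing home admissions) will then be multiplied" by the units each person used and summed into a total health care cost. Intervention cost is built separately by micro-costing. It includes personnel, and the activity diaries in 7.2 capture research nurse and staff time, training and supplies.

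The index stay is measured. Section 7.2, Data Collection, begins a list of items with "Upon discharge, length of stay, use of tethers", and names length of stay again under chart abstraction at discharge. No section attaches a price to it. Section 7.4.1 says that the Fam-FFC nurse "will work in the treatment units 20 hours a week for 14 months to implement the four components of the intervention".

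**The concern.** The accounting is asymmetric. Nurse, champion and staff time spent on the ward enters the sum; the consequence of that work for bed-days, as far as the text goes, does not. Much of Fam-FFC operates before discharge: unit education, environment and policy work, mentoring, daily bedside goals and the discharge checklist. Any of these could lengthen or shorten the stay. Section 7.2 also says that the care pathway varies with length of stay, so a longer stay could add counted nurse time while its extra days add nothing.

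At stake is whether the H5 estimate means what its name says. A programme that paid for itself partly through shorter stays could look like a net cost, and one that prolonged stays could look cheaper than it was.

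**Working it through.** The plan gives no cost figure to reproduce. The sample size used below is internally consistent: 6 units × 73 = 438 (section 8.2).

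**Step 1. Where could the index stay enter?**
- H4 (1.1): post-discharge services only. Not there.
- Health care cost (1.2 and 7.2): post-acute use, counted to six months after discharge. Not there.
- Utilization priced in 8.3: emergency room, hospital, long-term nursing home. No index-stay item is named, but the hospital item carries no time limit.
- Intervention cost in 8.3: six categories, none of them bed-days.
- H5 (1.1): no formula.

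The index stay is named in no component. Two places, H5 itself and the hospital item in 8.3, leave room to read it in.

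**Step 2. A cost that is counted, for scale.** Inputs: 20 hours a week for 14 months (7.4.1), taken as per site because the 14-month schedule in 7.2 is repeated at each site with one intervention unit; 73 patients per unit (8.2).
- Hours per site: 20 × 52/12 × 14 = 1,213.
- Hours per patient: 1,213 / 73 = 16.6.
- At an assumed wage of $40, $60 or $80 per hour: $665, $997 or $1,330 per patient.
- Supplies, up to $2,000 per site (7.2): 2,000 / 73 = $27 per patient.

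These hours cover all four components, including the 1 + 7 + 4 = 12 post-discharge contacts (7.2, 7.4.2), so they are not purely an in-hospital cost. They are also gross of whatever nurse time the control arm uses.

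**Step 3. The term left out, with day-based pricing.** Omitted term = difference in length of stay × cost per day. For an assumed half day:
- 0.5 × $1,000 = $500
- 0.5 × $2,000 = $1,000
- 0.5 × $3,000 = $1,500

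A full day doubles these, and the sign follows the sign of the stay difference.

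**Step 4. Stay difference equal to the nurse cost.** Days = nurse cost / cost per day.
- Lowest: 665 / 3,000 = 0.22 day
- Middle: 997 / 2,000 = 0.50 day
- Highest: 1,330 / 1,000 = 1.33 days

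**Step 5. Per-admission pricing.** Every patient has exactly one index admission, so at a common price the term is 1 × price in each arm and the difference is zero. Section 7.2 records both the number and the days of hospitalizations and mentions both charges and reimbursement rates. Section 8.3 does not say which unit is priced.

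**The case against.** The strongest reply is that the exclusion is inferred. H5 has no formula, and the hospital item in 8.3 has no time limit, so an analyst could include the index stay without departing from the text. That stands: a reader might infer that the plan expressly removes the index stay from H5, and it does not. What the documents support is that the natural reading omits it, because every statement of the utilization window points to discharge onwards.

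Second, a post-discharge window is a legitimate costing perspective, and the protocol declares it. For H4 that is a full answer. For H5 it is not, because H5 is framed as a total and counts ward-based delivery costs.

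Third, the size rests on an assumed wage, day cost and stay difference, with an average day cost applied to what may be a marginal half day. The pilot results in section 2.2 report no length-of-stay effect, and no hypothesis concerns it. That stands and limits the claim to a possibility.

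Fourth, there is one Fam-FFC and one control unit in each of three hospitals. A stay difference between three units and three units may reflect case mix or discharge practice, and pricing it would bring that imbalance into H5. This stands too. It argues for reporting both versions and against silent inclusion.

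**Conclusion.** The point holds in a limited form. H5 is undefined, and the plan followed as written would most naturally count the ward cost of Fam-FFC without any index-stay difference. With day-based pricing, a half-day difference ($500 to $1,500 per patient) is of the same order as the Fam-FFC nurse cost ($665 to $1,330), so it could change the H5 estimate in either direction. Wage, day cost and stay difference are all assumptions. With per-admission pricing the term is nil.

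A reader might go further and conclude that H5 will come out with the wrong sign. The documents do not support that: they give no expected effect on length of stay, no cost estimates, and no stated pricing unit. H4 is unaffected.

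**What to change.** In sections 7.2 and 8.3 (Aim 3):
- Define total cost for H5 as intervention cost + index-stay cost + post-discharge utilization to six months.
- Define index-stay cost as length of stay from unit admission × the same hospital day cost used for readmissions. Use one start point for both arms; enrolment is less suitable because consent can come up to 48 hours after unit admission (5.1.1.1).
- State the pricing unit. If hospital use is priced per admission, say so and note that the index-stay term then cancels.
- Keep H4 as post-discharge cost only.
- Report H5 with and without the index-stay term, and beside it the length-of-stay difference by arm, adjusted for site and the covariates already planned.

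The change adds one term from data already collected. Length of stay is skewed, so the H5 interval may widen. With three units per arm, a stay difference may partly reflect unit case mix or discharge practice, which is the reason for showing both versions.
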